4.3 Risk/Benefit

The safety monitoring practices employed by this protocol (e.g. complete ophthalmological exam, IOP monitoring, OCT, vital signs, hematology, serum chemistry, urinalysis, and AE questioning) are adequate to protect the subjects' safety.

There are also risks associated with the ophthalmic procedures required for participants in this study. However, these are all standard procedures that are widely performed in ophthalmology.

In the days following any IVT injection, patients are at risk of developing endophthalmitis. If the eye should become red, sensitive to light, painful, or develop a change in vision, the patient will be instructed to seek immediate care from an ophthalmologist. Other risks of IVT injection include traumatic cataract, retinal detachment and hemorrhage.

Transient increased IOP has also been identified as a risk following IVT injections. IOP will be carefully monitored in this study.

The approximately 150 mL of blood (See [Section 9.9](#)) planned for collection from each subject over the 18 months of the study does not pose an undue risk in this patient population.

Based on data available to date, IVT administration of complement C3 inhibitors does not seem to present an unreasonable ophthalmic or systemic risk to humans. In three previous clinical studies involving 72 subjects undergoing local C3 inhibition with the related compound POT-4/AL-78898A, no drug-related SAEs were reported. Also, a Phase I study with APL-2 in patients with wet AMD has completed and no drug-related SAEs have been reported thus far.

Following a routine scheduled interim review of this ongoing POT-CP121614 (FILLY) study, including data as of April 5, 2017, by the Safety Monitoring Committee, an imbalance in new exudation in subjects treated with APL-2 was observed (further details described in an Investigator Brochure Addendum No. 3, 10 April 2017). Higher rates in new exudation were observed in eyes treated with APL-2, particularly monthly. The risk of developing new exudation may be increased in patients with a prior history of exudative AMD in the fellow eye. Visual acuity in subjects who develop new study eye exudation does not appear to differ significantly from those who do not.

There is a potential health benefit for trial participants from receipt of study drug. We propose to administer APL-2 to patients with GA. If efficacious, APL-2 is expected to alter the course of GA and slow its rate of growth.

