### 3.4. TREATMENT ASSIGNMENT AND BLINDING

Each subject will be assigned a unique screening number upon entering screening. Subjects who complete the study screening assessments and meet all eligibility criteria will be scheduled to enter the study and be randomized. The randomization of subjects will be done via a web-based randomization system (IWRS) which will assign a unique randomization number. Subjects will be randomized in a 2:2:1:1 ratio to receive APL-2 monthly (AM), APL-2 every-other-month (AEOM), sham injection monthly (SM) or sham injection every-other-month (SEOM), respectively. The randomization will be stratified by site.

The study is single-masked. Subjects and assessors of efficacy assessments (imaging or visual acuity) are masked to treatment (APL-2 or sham injection). The investigators, site personnel not performing efficacy assessments, vendors, sponsor and CRO personnel will be unmasked to treatment assignment. Additionally the CRC, who will perform the independent review of efficacy evaluation images, will be masked to provide an objective assessment of these evaluations.

The independent SMC will be provided unmasked safety data for their safety assessment.

Masking will be maintained throughout the conduct of the study. In the event of a medical emergency where the knowledge of subject treatment by masked individuals (e.g. the subject or his/her physician) is required, an individual Investigator will have the ability to unmask the treatment assignment for a specific subject and share that information with the appropriate parties. The Investigator must endeavour to notify the Sponsor prior to unmasking a subject.

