### 6.4. SUBGROUPS

The following subgroups will be considered:

- Country: Australia, New Zealand and United States
- Reticular pseudodrusen at baseline: present, absent
- Age group: split into 3 similar sized groups (<75 years, 75-<85 years, ≥85 years)
- LL-VA deficit at baseline: < overall median value, ≥ overall median value
- Fellow-eye CNV at baseline: yes, no
- GA presence at baseline: unilateral, bilateral
- GA lesion size in the study eye: < 10 mm^2, ≥ 10 mm^2
- Sex: male, female

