### **8.2.2. Macular Neovascularization (MNV)**

The incidence and exposure adjusted incidence of macular neovascularization (MNV) TEAEs in the study eye will be summarized for the MITT population.

Exposure adjusted incidence (or incidence rate per 100-patient-years) = number of subjects experiencing MNV / total subject time at risk (in years) × 100

Total subject time at risk is the time from first study drug administration date to first MNV event date +1 for subjects who experience an event, or time from first study drug administration date to last visit date +1 for subjects who do not experience a MNV event. Total subject time will be presented in years with a year = 360 days for the calculation.

The incidence for the MITT population will be compared between the active treatment groups (APL-2 Monthly or APL-2 EOM) and sham group using a Fisher's exact chi-squared test. The analysis will be repeated by the subgroup fellow eye CNV at baseline.

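### The MNV analysis uses fellow-eye CNV only by repeating a crude test in subgroups, and never tests the order sham, EOM, monthly that the safety review reported

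*Protocol*

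**What the plan says.** Protocol 4.3 gives two observations from the Safety Monitoring Committee's review of this trial's data up to April 2017. On regimen: "Higher rates in new exudation were observed in eyes treated with APL-2, particularly monthly". On the fellow eye: "The risk of developing new exudation may be increased in patients with a prior history of exudative AMD in the fellow eye". It gives no rates.

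SAP 8.2.2 describes the MNV analysis. First, "The incidence and exposure adjusted incidence of macular neovascularization (MNV) TEAEs in the study eye will be summarized for the MITT population". Then, "The incidence for the MITT population will be compared between the active treatment groups (APL-2 Monthly or APL-2 EOM) and sham group"; the method is Fisher's test ("sham group using a Fisher's exact chi-squared test"). It ends: "The analysis will be repeated by the subgroup fellow eye CNV at baseline". SAP 6.4 defines that subgroup as "Fellow-eye CNV at baseline: yes, no".

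On allocation, SAP 3.4 states: "The randomization will be stratified by site". The ocular exclusions apply to the study eye only, so patients with fellow-eye CNV can enter, and nothing in the design balances them across arms.

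Monthly versus EOM is a listed comparison for GA area by FAF (SAP 8.1), BCVA (8.2.1), LL-BCVA (8.2.3), low-luminance deficit (8.2.4), distance from the fovea (8.2.5) and SD-OCT area (8.2.7). SAP 8.2.2 does not list it for MNV.

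**The concern.** New exudation is the safety signal that the protocol itself singles out, and the trial studies two injection frequencies in order to guide further development. Two questions follow: does the excess over sham persist once fellow-eye status is taken into account, and does risk rise with frequency? The plan approaches the first by splitting the sample and the second by tabulation alone.

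Three weaknesses result.

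- The overall comparison carries whatever imbalance in fellow-eye CNV chance produces, and no analysis combines the two strata to remove it.
- Tests run separately in two small strata are easily misread. Significance in one and not the other looks like effect modification even when the relative risk is the same in both.
- The reported ordering is never tested. The wording also leaves open whether the two APL-2 regimens are each tested against sham or pooled. A pooled test would remove the regimen contrast altogether.

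**Working it through.** **Inputs from the documents.** 80 monthly, 80 EOM and 80 pooled sham subjects (SAP 3.3); two-sided tests at 0.10 without multiplicity adjustment (SAP 6.1); 7 and 13 planned injections (SAP Table 1). The documents state no MNV rate, no MNV power and no prevalence of fellow-eye CNV, so there is no figure of the plan's own to reproduce.

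**Assumptions.** Fellow-eye CNV in 40%, varying at random between arms, and the MNV risks shown at each step. Full arms of 80 are used; a smaller MITT population would lower every power figure.

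**1. Chance imbalance.** The SD of the difference in CNV share between two arms is √(2 × 0.4 × 0.6 / 80) = 0.077, or 7.7 points. If risk differs by 10 to 20 points between strata, a 1-SD imbalance shifts the crude risk difference by 0.077 × 10 ≈ 0.8 to 0.077 × 20 ≈ 1.5 points. A 2-SD imbalance shifts it by 1.5 to 3.1 points. For comparison, the sampling SE of the risk difference at 3% versus 10% is √(0.03 × 0.97 / 80 + 0.10 × 0.90 / 80) = 0.039, or 3.9 points.

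**2. Repeated tests within subgroups.** Two cases, each with the same relative risk in both strata (simulated, Fisher's test at 0.10):

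| Risk without / with fellow-eye CNV | Relative risk | Power without | Power with |
|---|---|---|---|
| Sham 1% / 3%, APL-2 5% / 15% | 5 | about 12% | about 40% |
| Sham 2% / 8%, APL-2 6% / 24% | 3 | about 12-13% | about 46% |

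Significance in the CNV stratum alone therefore has a chance of about 0.40 × 0.88 = 35% in the first case and 0.46 × 0.87 = 40% in the second, although the relative effect does not differ between strata.

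**3. Does stratifying add power?** In the same two cases the crude test has about 53% power. An exact test stratified by fellow-eye CNV has 53-55% with doubled tails. Another two-sided convention gives 59%, but that convention also shows a gain of about 5 points (46% to 51%) when fellow-eye CNV is given no effect on risk (3% versus 10% in both strata). The apparent gain comes from how the p-value is defined, not from the adjustment.

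**4. Trend test.** Unstratified exact test, scores 0, 7 and 13, doubled tail, against a significant result in either pairwise Fisher test:

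| Risk sham / EOM / monthly | Either pairwise | Exact trend |
|---|---|---|
| 2 / 5 / 10% | 62% | 69% |
| 1 / 5 / 10% | 78% | 84% |
| 2 / 8 / 8% | 58% | 48% |
| 2 / 2 / 2% (null) | 2% | 5-6% |
| 5 / 5 / 5% (null) | 8% | 8% |

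The trend test stays below 10% in both null cases. Part of its advantage reflects Fisher's conservatism when events are few, as the 2% null row shows.

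Adding only the missing monthly versus EOM Fisher test would achieve little. Its power is 28%, 31%, 11% and 23% at 2/6/12%, 2/8/15%, 3/6/9% and 1/5/10%.

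**The case against.** A reader might infer that the plan overlooks both reported patterns. It does not. The last sentence of SAP 8.2.2 repeats the analysis by fellow-eye CNV, SAP 6.4 predefines that subgroup, SAP 6.1 has tables presented by regimen, and SAP 7.3 tabulates fellow-eye CNV by arm, so an imbalance would be visible.

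A reader might also call fellow-eye disease an established risk factor and the crude comparison biased. The protocol says only that risk may be raised and gives no rate. Randomisation leaves no systematic bias. What remains is chance imbalance, and its typical effect (0.8 to 1.5 points) is well below the sampling SE of 3.9 points.

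A third tempting claim is that stratifying buys power. Step 3 shows that it does not.

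On the trend test, the objection is that its benefit depends on the assumed shape, and that is right: it loses about 10 points if both regimens carry the same excess. The ordering was also seen in interim data from this same trial, and those events will be in the final analysis, so a significant trend cannot be independent confirmation. MNV is a secondary Phase II endpoint, and no decision rule depends on its p-value.

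These points reduce the weight of the concern. They do not supply a combined estimate, make the separate subgroup tests easier to read, or give the reported ordering a formal analysis.

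**Conclusion.** The point holds as a modest, optional improvement. SAP 8.2.2 uses a suspected risk factor only through subgroup repetition, and it plans no test of the ordering that the safety review reported.

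The strongest reason to stratify is interpretive: one common estimate guards against reading two low-powered tests (about 12% and 40-46%) as evidence of an effect only in patients with fellow-eye CNV. Protection against chance imbalance is a smaller benefit, and no power gain should be claimed. The trend test adds roughly 6 to 7 points of power when risk rises with frequency and loses about 10 when it does not, so it belongs beside the pairwise tests, as supportive evidence.

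The sizes rest on the assumed 40% prevalence and MNV risks, and on 80 per arm. That the combined estimate and the trend test are absent does not depend on any of these assumptions.

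**What to change.** In SAP 8.2.2:

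1. State that each APL-2 regimen is compared with pooled sham separately. For each, report the Mantel-Haenszel common risk difference stratified by fellow-eye CNV at baseline with its 95% CI, and an exact stratified test whose two-sided convention is named in advance. Keep the crude incidences and the subgroup tables as description.
2. Add, beside the pairwise tests and not in place of them, one exact trend test over sham, EOM and monthly with scores 0, 7 and 13. Describe it as supportive, because the ordering came from this trial's interim data.
3. State whether the SAP's fellow-eye CNV at baseline is meant to capture the protocol's prior history of exudative AMD in the fellow eye; the two descriptions are not identical.

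The cost is SAP wording and a few lines of code. Fellow-eye CNV is already a baseline variable, so no new data are needed. Two limits should be stated: the trend test is weaker if both regimens carry equal risk, and, like the pairwise tests, it is affected by the monthly arms having more visits at which MNV can be found.

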5. STUDY OBJECTIVES AND ENDPOINTS

5.1 Study Objectives

The primary objectives of the study are to assess the safety, tolerability and evidence of activity of multiple IVT injections of APL-2 in subjects with GA associated with Age-Related Macular Degeneration in order to support further development into confirmatory Phase III studies.

5.2 Study Endpoints

5.3 Primary Efficacy Endpoint

To demonstrate superiority of monthly and EOM APL-2 IVT injections compared to sham injections based upon the mean change in GA lesion size as measured by FAF.

- The primary endpoint is the change in square root GA lesion size from baseline to Month 12 as measured by FAF.

5.4 Primary Safety Endpoint

- Number and severity of local and systemic treatment emergent adverse events

5.5 Secondary Endpoints

Comprehensive but not limiting lists of secondary efficacy, safety and pharmacokinetic endpoints are presented in the Synopsis, [Section 1](#).

6. PATIENT POPULATION

The study population includes approximately 240 subjects to be enrolled at approximately 40 multinational sites. To participate in the study, subjects must be diagnosed with GA of the macula associated with AMD in one or both eyes. If both eyes meet the criteria and qualify for the study, the eye with the worst visual acuity at the screening visit will be designated as the study eye. If both eyes have the same visual acuity, the right eye will be used as the study eye. The complete inclusion and exclusion criteria are presented in the Synopsis, [Section 1](#).

6.1 Women of childbearing potential:

WOCBP are defined as pre-menopausal women physiologically capable of becoming pregnant.

6.2 Women non-childbearing potential:

WONCBP are defined as women meeting any of the following criteria:

- Older than 45 years with amenorrhea for > 2 years or older than 60 years with amenorrhea for > 1 year. Both confirmed by FSH and LH levels.
- Has undergone hysterectomy,
- Has undergone bilateral oophorectomy,
- Has undergone bilateral salpingectomy.

6.3 Approved methods of contraception

Approved methods of contraception include: oral contraceptives, intrauterine device, medically acceptable barrier methods (i.e. condom), implantable or injectable contraceptives or removable birth control device. Subjects practicing abstinence and coitus interruptus (pull out method) must agree to use an approved method of contraception during the study.

7. TREATMENT OF SUBJECTS

7.1 Allocation to Treatment

Each subject will be assigned a unique screening number before screening. Subjects who complete the study screening assessments and meet all the eligibility criteria will be scheduled to enter the study and randomized on Day 0 in a 2:2:1:1 manner to receive treatment with APL-2 Monthly (AM), APL-2 Every-Other-Month (AEOM), Sham injection Monthly (SM) or Sham injection Every-Other-Month (SEOM), respectively. The randomization scheme will be generated and maintained by the Sponsor. The randomization schedule will be blocked to ensure a balance of study treatment allocations within investigational sites.

7.2 Masking and Minimization of Bias

The intent of masking is to limit the occurrence of conscious and unconscious bias in the conduct and interpretation of the clinical study. Bias could arise from the influence that the knowledge of a specific treatment assignment may have on the recruitment and allocation of subjects, their subsequent care, the assessment of end points, the handling of withdrawals, and so on. The essential aim of masking, therefore, is to prevent identification of the treatments by the subject and the masked assessors associated with the conduct of the study until all such opportunities for bias have passed.

This single-masked study is subject-masked and assessor masked, with subjects randomized to either APL-2 or Sham Injection, as well as to a monthly or EOM treatment schedule for 12 months. To prevent bias in treatment assignment, eligible patients will be randomized using a web-based randomization system. The subject and assessors (photographer(s) and visual acuity technicians) will be masked to the specific treatment being administered. The Investigators (including Sub-Investigators), site personnel not performing assessments of efficacy variables (imaging and visual acuity), vendors and Sponsor (or Contract Research Organization (CRO)) personnel will be unmasked to treatment assignment. Additionally, a masked independent review of SD-OCT, FAF, DCFP and FA images will be performed at the CRC to provide an objective assessment of these evaluations.

This level of masking will be maintained throughout the conduct of the study. In the event of a medical emergency where the knowledge of subject treatment by masked individuals (e.g. the subject or his/her physician) is required, an individual Investigator will have the ability to unmask the treatment assignment for a specific subject and share that information with the appropriate parties. The Investigator must endeavor to notify the Sponsor prior to unmasking a subject. The independent SMC will be provided unmasked safety data for their safety assessment.

7.3 Treatments Administered

7.3.1 Dose Levels and Study Arms

A single dose of 15 mg APL-2/100 μ L will be tested in this study. Subjects will receive multiple IVT injections as outlined in the table below

Treatment Arms
APL-2 15 mg/100 µL Monthly for 12 months (13 injections)
APL-2 15 mg/100 µL EOM for 12 months (7 injections)
Sham Monthly for 12 months (13 sham injections)
Sham EOM for 12 months (7 sham injections)

7.3.2 Drug supplies

7.3.2.1 Identity of Investigational Product

APL-2 will be supplied as a lyophilized powder in stoppered glass vials and should be stored at -20°C and according to the label. Lyophilized APL-2 must be reconstituted prior to the IVT injection. Specific instructions for preparing APL-2 for the IVT injection procedure are provided in the Manual of Procedures (MOP).

7.3.2.2 Accountability

APL-2 drug product will be provided to a designee at the study site and must be stored in a pharmacy or otherwise locked and secured, at temperature of -20 °C (i.e. frozen). The drug product supply is accessible only to those individuals authorized by the PI. The Sponsor will supply sufficient quantities of APL-2 drug product to allow completion of this study.

Designated study staff will provide the study treatments to the subjects in accordance with their assigned subject numbers and the randomization schedule. During the study, the receipt of the drugs supplied at the clinical site and of study treatment dispensation for each subject will be documented in drug accountability records. These drug accountability records are to be kept separate from the patient medical records and other source documents.

All used vials should be retained by the clinical site until drug accountability monitoring is performed and then returned to the Sponsor or designee, or destroyed per Sponsor instructions. At the conclusion of the study, any unused investigational product will be retained by the clinical site, returned to the Sponsor or designee, or destroyed per Sponsor instructions, and this will be documented in the drug accountability records.

7.3.3 Intravitreal APL-2 Administration

Subjects receiving active treatment will be administered a 100 µL IVT injections of APL-2 using a 29G or 27G thin wall needle, at the discretion of the PI. Detailed instructions on drug preparation, pre-injection procedures, administration of APL-2, and post-injection procedures are provided in the MOP. The procedure for sham injection will be the same as that used for IVT injection until the actual injection; no actual injection will occur. Detailed instructions on sham injection procedures are provided in the MOP.

Clinic staff involved in the injection tray assembly, anesthetic preparation, and study drug preparation and administration will follow appropriate aseptic techniques to minimize the risk of potential adverse events associated with IVT injections (e.g. endophthalmitis).

To minimize IOP elevation after IVT injection of APL-2, decompression of the eye must be performed before all APL-2 injections. This is done by applying moderate pressure to the globe with cotton swabs for 30-60 seconds during anesthetic preparation.³¹

In addition to the procedures outlined in the MOP, adherence to specific institutional policies associated with IVT injections will be observed.

7.4 Concomitant Therapies

Any concomitant medications a participant is receiving at the start of the study or that are given for any reason during the study (except for routine medications given for ocular procedures required by the protocol, such as topical anesthetic) must be recorded in the source document and CRF including start and stop date and time, dose, route, and indication. In addition, all ocular and non-ocular procedures such as surgical procedures (excluding study treatment procedures) must also be recorded in the source document including start and stop dates. Surgical anesthetics, paramedical or alternative therapies (e.g. acupuncture, massage) should also be recorded in the source documents and CRF.

Metoclopramide or other agents to prevent nausea induced by fluorescein injection may be administered at the discretion of the PI.

7.4.1 Endophthalmitis Treatment

The decision to treat a participant for endophthalmitis or suspected endophthalmitis will be guided by the clinical judgment of the PI. The treatment method (*pars plana* vitrectomy vs. vitreous tap) and choice of antimicrobial agents are also at the discretion of the PI and should follow current standard practice patterns. The decision to use IVT steroids (e.g. dexamethasone) for the treatment of endophthalmitis is also at the discretion of the PI.

